9.5.2. Analysis for Electrocardiograms Parameters

For each ECG parameter in Table 11, the number and percentage of patients who met each potentially clinically significant criterion will be summarized.

Investigator's clinical interpretation of the 12-lead ECG results (normal or abnormal) will be tabulated to present shift from baseline to the worst case post-dose during the treatment period. Similarly, a shift table from baseline to the last post-baseline assessment during the treatment period will be generated.

All ECG parameters as collected along with corrected values of QTcF will be included in the data listing. In the listing, the flag of meeting a PCS criterion and the flag indicating investigator's determined abnormality are also included.

G1 Therapeutics

10. CHANGES FROM THE PROTOCOL

- Approximately 45 patients were planned to be enrolled per Protocol Version 2.0. The sponsor decided to close enrollment to this study on February 14, 2023 in order to reallocate resources to other ongoing trilaciclib clinical trials. The final total number of patients enrolled in this study is 30.
- The protocol has defined two planned analyses. The first planned analysis, analyses for progression free survival, tumor response endpoints, and myeloproctection endpoints, were to be conducted when approximately 80% of the patients have radiographically determined disease progression or have died. The final planned analysis is to be conducted when approximately 70% of patients have died. The first planned analysis was not officially conducted as planned and was combined with the the final planned analysis (see Section 2.1).
- The following secondary objectives, intended to evaluate the myeloprotective effects of Trilaciclib when administered prior to SG, were not conducted as part of the final analysis as they were not deemed critical for the aCSR:
 - o Occurrence and number of RBC transfusions on/after Week 5
 - Occurrence of ESA administration
 - Occurrence of Grade 3/4 decrease of platelets
 - Occurrence and number of platelet transfusions
 - Occurrence of serious infections
 - Use of IV antibiotics
- The protocol mentions the collection of ECOG performance status information. The summary and listing of these data was deemed non-critical and will not be included for the aCSR.
- The change from baseline summaries for laboratory assessment will not be included for the aCSR.

G1 Therapeutics

11. **REFERENCES**

Wu, Jianrong. Sample size calculation for the one-sample log-rank test. Pharmaceutical Statistics. 2015;Volume 14:26-33.

G1 Therapeutics

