G1T28-213

anti-tumor efficacy results. For a more detailed description of the results, refer to the trilaciclib IB.

Results from the TNBC Study G1T28-04 demonstrated that although the addition of trilaciclib at the US FDA approved dose of 240 mg/m² to GC did not statistically significantly improve chemotherapy-induced myelosuppression as measured by the neutrophil-based endpoints of DSN in Cycle 1 and occurrence of SN, there were trends toward improvement in RBC and platelet-based measures. In addition, anti-tumor efficacy results demonstrated a clinically meaningful improvement in PFS and OS (Figure 4; Table 3). This meaningful anti-tumor efficacy was observed across multiple subgroups, including both PD-L1 positive and negative tumor types (Table 4), and in both trilaciclib groups compared with the control group.

As mentioned in Section 4.3.1.1, there is a hypothetical risk that administration of trilaciclib prior to chemotherapy could decrease chemotherapy efficacy. This hypothetical risk is countered by the results observed in Study G1T28-04 which suggested that the addition of trilaciclib improves the anti-tumor efficacy of GC regardless of the CDK4/6 status of the TNBC tumor. Although TNBC tumors are predominantly classified as CDK4/6 independent (i.e., their replication is not sensitive to CDK4/6 inhibition), there is a small subset of patients whose tumors are classified as either CDK4/6 indeterminate or CDK4/6 dependent. When the TNBC population enrolled in Study G1T28-04 is divided into these subsets, evaluation of the anti-tumor efficacy in patients whose tumors are classified as CDK4/6 indeterminate or CDK4/6 dependent suggests that trilaciclib does not antagonize the anti-tumor effects of GC. Specifically, PFS and OS did not decrease when trilaciclib was added to GC in the most CDK4/6-dependent population (see trilaciclib IB).

G1T28-213

Table 3: G1T28-04: Summary of Overall Survival and Progression-Free Survival (ITT Analysis Set)

Category	Group 1 Gem/Carbo (Day 1+8) (N=34)	Group 2 Gem/Carbo + Trilaciclib (Day 1+8) (N=33)	Group 3 Gem/Carbo + Trilaciclib (Day 1/2+8/9) (N=35)	Groups 2+3 (N=68)	
Overall survival (months) (95% (	CI) a, b				
25%	5.8 (2.8, 9.7)	9.4 (3.4, 19.6)	8.8 (6.0, 15.3)	8.8 (6.0, 14.0)	
Median	12.6 (6.3, 15.6)	NR (10.2, NR)	17.8 (12.9, 32.7)	19.8 (14.0, NR)	
75%	17.8 (12.8, 25.0)	NR (NR, NR)	32.7 (19.8, NR)	NR (32.7, NR)	
Comparison (treatment group ve	rsus Group 1)				

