## 5. OBJECTIVES AND ENDPOINTS

The primary, secondary, and exploratory objectives of this study, and their associated endpoints, for patients who received at least 2 prior treatments, at least 1 in the metastatic setting for unresectable, locally advanced or metastatic TNBC being administered trilaciclib with sacituzumab govitecan-hziy, are presented in Table 5.

Table 5: Objectives and Endpoints

Objectives	Endpoints
Primary Objective	
To evaluate the anti-tumor activity of trilaciclib when administered prior to sacituzumab govitecan-hziy	PFS defined as time from the date of first dose of study drug to radiographic disease progression using RECIST v1.1 or death due to any cause, whichever occurs first; for patients without disease progression or death, PFS will be calculated per censoring rules.
Secondary Objective: Efficacy	
To evaluate the anti-tumor activity of trilaciclib when administered prior to sacituzumab govitecan-hziy	
 
ORR defined as the percentage of patients with BOR of confirmed CR or confirmed PR per RECIST v1.1
 
CBR defined as the percentage of patients with a BOR of confirmed CR, confirmed PR, or SD lasting 24 weeks or longer since the first date of study drug administration per RECIST v1.1
 
DOR defined as duration of objective response
 
OS defined as time from the date of first dose of study drug to death due to any cause for those who died; or time to last contact known as alive for those who survived in the study (censored cases)
 

Secondary Objective: To evaluate the myel-	oprotective effects of trilaciclib
To evaluate the myeloprotective effects of trilaciclib when administered prior to sacituzumab govitecan-hziy	
 
Occurrence of SN (during Cycles 1/2 and overall study)
 
Occurrence of febrile neutropenia
 
Occurrence of G-CSF administration
 
Occurrence of Grade 3/4 decrease of hemoglobin
 
Occurrence and number of RBC transfusions on/after Week 5
 
Occurrence of ESA administration
 
Occurrence of Grade 3/4 decrease of platelets
 
Occurrence and number of platelet transfusions
 
Occurrence of serious infections
 
Use of IV antibiotics
 

G1T28-213

Objectives	Endpoints
Secondary Safety Objectives	

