# 6.6. Rationale for Supportive Care Interventions (Growth Factors and Transfusions)

In order to facilitate an unbiased evaluation of trilaciclib effects on the hematologic endpoints, primary prophylactic granulocyte colony-stimulating factor (G-CSF) will be prohibited in Cycle 1; however therapeutic G-CSF (administered in response to a neutropenic event) in Cycle 1 and secondary prophylactic G-CSF beginning in Cycle 2 and for all subsequent cycles (i.e., after a precipitating event in a prior cycle of therapy) will be allowed per growth factor/neutropenia management guidelines in Section 9.4.1 and Investigator discretion (Aapro, 2010; Smith, 2015).

Erythropoiesis-stimulating agent (ESA) administration and RBC or platelet transfusions will be allowed per Investigator discretion based on guidelines detailed in Section 9.4.2 and Section 9.4.3. While these interventions may confound analysis of the myelosuppression endpoints, allowing physicians to provide appropriate supportive care to patients will facilitate patient safety.

The NCCN Human Growth Factor Supported Care Guidelines (NCCN, 2021) for patients receiving cytotoxic chemotherapy (including those in clinical trials) includes the following guidance for the use of trilaciclib as a supportive care intervention for patients with ES-SCLC. Trilaciclib as a supportive care intervention is being further investigated in this trial in patients with TNBC receiving sacituzumab govitecan-hziy treatment.

- Trilaciclib may be used as a prophylactic option to decrease the incidence of chemotherapy-induced myelosuppression when administered before (or G-CSF may be administered after) platinum/etoposide ± immune checkpoint inhibitor-containing regimens or a topotecan-containing regimen for ES-SCLC.
- Trilaciclib may be used as a prophylactic option to decrease the incidence of chemotherapy-induced myelosuppression when administered before (*prophylactic* G-CSF may be administered after *Cycle 1*) platinum/etoposide ± immune checkpoint inhibitor-containing regimes or a topotecan-containing regimen for ES-SCLC.
- Trilaciclib may be used as a prophylactic option to decrease the incidence of anemia and RBC transfusions when administered before platinum/etoposide ± immune checkpoint inhibitor-containing regimens or a topotecan-containing regimen for ES-SCLC.

G1T28-213

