1.2. Study Objectives

Primary:

To evaluate the anti-tumor efficacy of trilaciclib when administered prior to sacituzumab govitecan-hziy as measured by progression free survival (PFS).

Secondary:

To evaluate the anti-tumor efficacy of trilaciclib administered prior to sacituzumab govitecanhziy as measured by the objective response rate (ORR), duration of objective response (DOR), clinical benefit rate (CBR), and overall survival (OS); evaluate the myeloprotective effects of trilaciclib; and assess the safety and tolerability of trilaciclib administered prior to sacituzumab govitecan-hziy.

Specifically, the primary and secondary objectives and their associated endpoints are described in Table 1.

Objectives	Endpoints	
Primary Objective		
To evaluate the anti-tumor activity of trilaciclib when administered prior to sacituzumab govitecan-hziy	• PFS defined as time from the date of first dose of study drug to radiographic disease progression using RECIST v1.1 or death due to any cause, whichever occurs first; for patients without disease progression or death, PFS will be calculated per censoring rules.	
Secondary Objective: Efficacy		
To evaluate the anti-tumor activity of trilaciclib when administered prior to sacituzumab govitecan-hziy	 ORR defined as the percentage of patients with BOR of confirmed CR or confirmed PR per RECIST v1.1 CBR defined as the percentage of patients with a BOR of confirmed CR, confirmed PR, or SD lasting 24 weeks or longer since the first date of study drug administration per RECIST v1.1 DOR defined as duration of objective response OS defined as time from the date of first dose of study drug to death due to any cause for those who died; or time to last contact known as alive for those who survived in the study (censored cases) 	
Secondary Objective: Myeloprotective eff	fects of trilaciclib	
• To evaluate the myeloprotective effects of trilaciclib when administered prior to sacituzumab govitecan-hziy	 Occurrence of SN (during Cycles 1/2 and overall study) Occurrence of febrile neutropenia Occurrence of G-CSF administration 	

Table 1Primary and Secondary Objectives and Endpoints

Objectives	Endpoints	
Secondary chiestiyes: Sefety	 Occurrence of Grade 3/4 decrease of hemoglobin Occurrence and number of RBC transfusions on/after Week 5 Occurrence of ESA administration Occurrence of Grade 3/4 decrease of platelets Occurrence and number of platelet transfusions Occurrence of serious infections Use of IV antibiotics 	

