8.1.4. Secondary Efficacy Endpoint – Myeloprotection Efficacy Endpoints

Secondary myeloprotection endpoints that are defined to assess trilaciclib's effect on multiple lineage protection during the treatment period are described in Table 7 by lineage (i.e., neutrophils, and red blood cells [RBCs]). Endpoints that evaluate trilaciclib's impact on study drug delivery during the treatment period are also described in Table 7.

Unless otherwise specified, all endpoints described in Table 7 are derived based on data collected through scheduled and unscheduled visits during the treatment period.

Lineage	Endpoint	Type of Variable		
Neutrophils	Occurrence of severe neutropenia (during cycles 1/2 and overall study)	Binary		
	Occurrence of febrile neutropenia			
	Occurrence of G-CSF administration	Binary		
RBCs	Occurrence of Grade 3 or 4 decreased hemoglobin	Binary		
Dose Modifications	Occurrence of SG dose reduction	Binary		
	Number of SG dose reductions (event rate per 100 cycles)	Counting		
	Occurrence of cycle delay due to hematologic toxicity	Binary		
	Number of cycle delays due to hematologic toxicity (event rate per 100 cycles)	Counting		

Table 7Myeloprotection Endpoints

G-CSF=granulocyte colony stimulating factor; RBC=red blood cell, SG= sacituzumab govitecan-hziy..

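### SAP Section 10 drops six of ten planned myeloprotection endpoints for a reporting reason only; the real loss is transfusion and ESA use, which the retained hemoglobin endpoint needs for its interpretation

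*SAP*

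**What the plan says.** Protocol Section 5 (Table 5) gives ten endpoints for the myeloprotection objective, from severe neutropenia to IV antibiotic use. SAP Section 1.2 (Table 1) repeats all ten as secondary, including "Occurrence and number of RBC transfusions on/after Week 5".

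SAP Section 10 names six of the ten and states that they "were not conducted as part of the final analysis as they were not deemed critical for the aCSR". No other reason is given.

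SAP Table 7 keeps severe neutropenia, febrile neutropenia, G-CSF use and Grade 3/4 hemoglobin. It also keeps sacituzumab govitecan dose reductions and cycle delays due to hematologic toxicity. SAP 8.1.4.2 defines the hemoglobin endpoint as at least one value below 8.0 g/dL.

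On ESA use and transfusions, protocol 6.6 says: "While these interventions may confound analysis of the myelosuppression endpoints", allowing them serves patient safety.

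**The concern.** The six endpoints were specified in the protocol and are removed in the SAP of a single-arm, open-label study whose enrollment had already closed. The reason concerns the scope of an abbreviated report. It is not a matter of data quality or feasibility. Nothing says when the choice was made, or what data the people making it had seen.

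The set that remains is also lopsided. Severe neutropenia stays next to its supportive-care counterpart, G-CSF use. Hemoglobin stays without its counterparts, transfusion and ESA use. A low rate of Grade 3/4 hemoglobin could then mean that the lineage was protected, or that patients were treated before reaching the threshold, and Table 7 could not tell the two apart.

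The dropped items also matter to the rationale. For the earlier TNBC trial, which found no statistically significant neutrophil benefit, protocol 4.3.2.1 reports that "there were trends toward improvement in RBC and platelet-based measures".

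**Working it through.** There is no power, event or alpha figure to reproduce. The check is an item-by-item comparison of protocol Table 5, protocol 12.4.6.3, SAP Table 7 and the rest of the SAP.

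| Endpoint | Protocol Table 5 | Protocol 12.4.6.3 | SAP Table 7 | Elsewhere in the SAP |
|---|---|---|---|---|
| Severe neutropenia | yes | yes | kept | |
| Febrile neutropenia | yes | yes | kept | |
| G-CSF use | yes | yes | kept | |
| Grade 3/4 hemoglobin | yes | yes | kept | |
| RBC transfusions (occurrence, number) | yes | yes | dropped | no dedicated summary |
| ESA use | yes | yes | dropped | ATC/PT medication row (5.4) |
| Grade 3/4 platelets | yes | yes | dropped | highest grade and Grade 3-4 (9.3.2); thrombocytopenia AEs by grade (9.2.3) |
| Platelet transfusions (occurrence, number) | yes | yes | dropped | no dedicated summary |
| Serious infections | yes | no | dropped | serious AEs by SOC and PT (9.2.3) |
| IV antibiotics | yes | no | dropped | ATC/PT medication row, route not separated (5.4) |
| Dose reductions | no | yes | kept | |
| Dose delays | no | yes | kept, as hematologic cycle delays | |

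**Share dropped**
- Against protocol Table 5: 6/10 = 60%.
- Against protocol 12.4.6.3: 4/10 = 40%.
- Against both lists combined: 6/12 = 50%.
- Counting occurrence and number separately: 8/12 = 67%, 6/14 = 43% and 8/16 = 50%.

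**What is lost in substance**
- Grade 3/4 platelets is in effect still computed. SAP 9.3.2 summarizes Grade 3-4 for each hematology parameter, SAP 9.1 includes unscheduled values, and the safety population has the same definition as the FAS (SAP 3.1, 3.3).
- The two transfusion endpoints have no replacement. Protocol 9.5 collects blood products together with medications, so a transfusion might surface as a coded row. The SAP plans no Week 5 window, count or rate for it.
- SAP 8.2.4.2 still provides for event rates per 100 weeks, but every counting endpoint left in Table 7 is per 100 cycles. Protocol 12.4.6.3 uses RBC transfusions on or after Week 5 as its example of a rate per 100 weeks.

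**Why hemoglobin is hard to read alone**
Protocol 9.4.2 allows ESAs once hemoglobin is below 10 g/dL. Protocol 9.4.3 leaves transfusion of symptomatic patients to the investigator at any hemoglobin level. A patient treated between 8.0 and 10 g/dL who never falls below 8.0 counts as no event. Assume that all 30 enrolled patients were dosed and that k of them were kept above 8.0 in this way. The reported proportion is then lower by k/30: 1/30 = 3.3 percentage points for k = 1, and 5/30 = 16.7 points for k = 5. The documents do not give k. Transfusion and ESA counts would show how large it could be.

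**The case against.** The strongest reply is that most of the information survives. A reader might infer from Section 10 that the objective has lost all its platelet and infection evidence. It has not. Platelet grades, thrombocytopenia AEs and serious AEs stay in the safety tables, and low-platelet delays count in a retained Table 7 endpoint (SAP 8.1.4.3). This stands, and it confines the loss to transfusions and the dedicated ESA, serious-infection and IV-antibiotic rows.

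A reader might also take the multiple-lineage wording in SAP 8.1.4 as a platelet claim that Table 7 cannot support. The same sentence limits itself: the endpoints are "described in Table 7 by lineage (i.e., neutrophils, and red blood cells [RBCs". The reduced scope is stated openly.

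The share dropped depends on the list. Protocol 12.4.6.3 omits the two infection items and adds the dosing endpoints that Table 7 keeps, so 60% is the Table 5 figure only.

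The reply also points to general cutting back: enrollment was closed to reallocate resources, the report is abbreviated, and Section 10 also drops ECOG and laboratory change-from-baseline summaries. Favourable selection would not obviously keep the neutrophil endpoints, where the earlier TNBC trial found no significant benefit, and drop most of the RBC and platelet endpoints, where it saw trends. That is a fair point against assuming intent.

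Finally, the summaries are descriptive and have no comparator. Even all ten could not establish protection, and adding separate transfusion and ESA rows gives context without removing confounding. This stands too, but it does not justify leaving the context out.

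**Conclusion.** The point holds in a limited form. Six of the ten Table 5 endpoints (four of ten on the 12.4.6.3 list) leave the efficacy analysis for a reporting reason, while SAP Table 1 still presents all ten as secondary. The material loss is the RBC and platelet transfusion endpoints, followed by the ESA, serious-infection and IV-antibiotic rows. The main consequence is that the retained hemoglobin endpoint is harder to interpret.

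A reader might infer outcome-reporting bias, or a choice made after database lock. The documents support neither. The SAP text postdates the enrollment closure of 14 February 2023, and its 202309 drug-dictionary label suggests about September 2023 or later. SAP 2.1, however, still places the lock in the future, and the omission is disclosed in the section meant for changes. Against that, Section 10 speaks of the omission in the past tense and no data-access statement is given. Selective reporting therefore remains an open risk. No test or error rate is affected.

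This conclusion assumes that transfusion and ESA data were collected as protocol 9.5 requires, and that no transfusion summary sits in a programming document outside the SAP.

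**What to change.** Restore the six endpoints to SAP Table 7 as n (%) on the FAS. Following protocol 12.4.6.3, report RBC transfusions on or after Week 5 also as events per 100 weeks, and give platelet transfusions a rate with its unit stated. Carry the platelet-grade row over from the SAP 9.3.2 output. Remove the matching bullets from Section 10 so that it agrees with Table 1.

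At minimum, restore RBC transfusions, platelet transfusions and ESA use. For any endpoint still left out, state when the choice was made and with what access to data, name the safety table that carries the related information, and mark the omission in Table 1.

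The cost is about eight descriptive rows (four single endpoints plus occurrence and number for two: 4 + 2 × 2 = 8) for 30 patients, from data the protocol already collects. One item needs more than programming: serious infection has no definition for this endpoint, so the SAP must state one.

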12. APPENDICES

G1 Therapeutics

APPENDIX 1. SCHEDULE OF ASSESSMENTS

Table 12Schedule of Assessments

		Treatment Phase (1 cycle = 21 days)			Follow-Up Phase		
	Screening	Every C	ycle	End of Treatment Visit	Safety Follow-up	Survival Follow-Up	
Assessment	30 days prior to enrollment	Day 1	Day 8	14 days after last dose of study treatment (±7d)	30 days after last dose (+7d)	Every 3 months post-Safety Follow-up	See Protocol Section for Additional Details
Informed Consent	Х						Section 13.3
Enrollment		X [Cycle 1 (-7d)]					Section 11.1.2
Inclusion/Exclusion Criteria	Х						Section 7
Demographics	Х						Section 11.1.3
Medical History and Surgical History	Х						Section 11.1.4
Concomitant Medications	Х		Х				Section 11.1.4
Complete Physical Examination (include weight and height)	Х						Section 11.3.2
Symptom-directed Physical Examination (with weight only)		X					Section 11.3.2
Vital Signs	Х	X		X			Section 11.3.1
ECOG Performance Status	Х	X		X			Section 11.3.3
Adverse Event Reporting			Х		X		Section 11.3.6
Laboratory Assessments and Procedures							
Hematology	Х	X	Х	X			Section 11.3.5

		Treatment Phase (1 cycle = 21 days)			Follow-Up Phase		
	Screening	Every C	Cycle	End of Treatment Visit	Safety Follow-up	Survival Follow-Up	
Assessment	30 days prior to enrollment	Day 1	Day 8	14 days after last dose of study treatment (±7d)	30 days after last dose (+7d)	Every 3 months post-Safety Follow-up	See Protocol Section for Additional Details
Chemistry	Х	X ^a		Х			Section 11.3.5
Pregnancy Test (WOCBP only)	Х	Х		Х			Section 11.3.5
12-lead Electrocardiogram (in triplicate)	Х	X [Cycle 1]	X [Cycle 1]				Section 11.3.4
Study Treatment							
Trilaciclib		Х	Х				Section 9.1
Sacituzumab govitecan-hziy		Х	Х				Section 9.1
Disease Assessment							
Tumor Assessments (CT/MRI)	Х		X ^b				Section 11.2.1
Survival Follow Up and Subsequent Anti-Cancer Treatments						Х	Section 11.7

CR=complete response; CT=computed tomography; d=day; ECG=electrocardiogram; ECOG=Eastern Cooperative Oncology Group;

FDG=[¹⁸F]-fluorodeoxyglucose; MRI=magnetic resonance imaging; NaF=sodium fluoride; PET=positron emission tomography; MRI=magnetic resonance imaging; Q6=every six; Q9=every 9; WOCBP=women of childbearing potential

^a Chemistry samples will be collected every cycle during Cycles 1-4 and every other cycle (Cycle 6, Cycle 8, etc.) if results are stable, per Investigator discretion.

^b CT/MRI of chest/abdomen/pelvis Q6 weeks (± 7d) through Week 36 relative to Cycle 1 Day 1 and Q9 weeks (± 7d) thereafter relative to Cycle 1 Day 1 until documented disease progression or subsequent anticancer therapy. Brain scan (MRI preferred) during screening is not required and should be performed per Investigator discretion based on clinical signs and symptoms. Additional brain MRI should be conducted if there are new clinical signs and symptoms suggestive of brain metastases. Bone metastases identified at baseline via a bone scan or PET (such as FDG-PET, NaF-PET, or other locally available PET options) to be followed at scheduled visits using localized CT or MRI as clinically indicated. If bone metastases cannot be seen on CT or MRI scans, bone scans or PET should be repeated, using the same diagnostic procedure bone metastases were at baseline, when CR is identified in target disease or when progression in bone is suspected.

Г

